- The subject has active infection processes, that in the opinion of the investigator may compromise safety or study objectives
- The subject is known to have a pre-existing condition that may interfere with wound healing, e.g. malignancy, diabetes or autoimmune disease, immunocompromised blood borne diseases, has AIDS, is HIV or Hepatitis-A positive, or currently has a severe dermatological disorder (e.g. severe psoriasis, epidermolysis bullosa, pyoderma gangrenosum)
- The subject has other concurrent conditions that in the opinion of the investigator may compromise safety or study objectives
- The subject has a known hypersensitivity to Trypsin and/or Compound Sodium Lactate for Irrigation (Hartmann's) solution
- The subject cannot be compliant with study procedures and that, in the investigator's opinion, would interfere with the study objectives

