placement of the primary dressing, a secondary dressing, Xeroform™ Petrolatum Gauze (Covidien, USA) will be applied to keep wounds moist then area will be wrapped with bulk dressing (e.g. gauze) to protect the wound surface, with or without an adhesive retention dressing as clinically indicated. The primary and secondary dressings should remain in situ for a minimum of 6 to 8 days and are not to be manipulated until the first post-operative visit unless medically necessary.

The donor area will be dressed in the following manner: The primary dressing will be Xeroform™ Petrolatum Gauze (Covidien, USA). The area will then be wrapped with bulk dressing (e.g. gauze) plus or minus a compressive wrap (ace-wrap) based on the area of harvest (extremity vs torso). The donor area bulk dressing will be removed at 48 hours. The primary dressing (Xeroform™ Petrolatum Gauze) will remain in place and be gradually peeled off over several days.

The primary dressing can be trimmed and removed as the Telfa™ Clear lifts from the wound bed. Under no circumstances will the primary dressing be forcibly removed; the Telfa™ Clear should be allowed to fall off on its own accord. If the Telfa™ Clear dressing hasn't fallen off in 3 weeks, only at this time point can it be moisten to peel off. It is essential that any dressing not easily removed be soaked in aqueous or oil-based solutions to prevent trauma upon removal. Once the primary dressing has been removed, a dressing of the investigator's choice will be applied to protect the wound surface, with or without an adhesive retention dressing as clinically indicated. All dressing regimens, dressing changes and dressing types will be recorded on the eCRF. Once the wounds are determined to be healed, therapy will be applied that is consistent with the standard of care at the clinical site.

Any dressing used other than Telfa™ Clear as primary dressing and Xeroform™ Petrolatum Gauze as secondary dressing at the treatment site areas prior to wound healing will be considered a protocol deviation.

Negative pressure wound therapy (NPWT) (i.e. wound vac) will not be reapplied after treatment with ReCell as this may compromise the treated area by removing the applied cells.

Post-Operative Care:

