A subject may withdraw consent and discontinue participation in the study at any time and for any reason without penalty, if he/she wishes to do so. The investigator may also withdraw a subject if continuing participation is believed to be harmful to the subject’s well-being or in the event of protocol violations, non-compliance (i.e. loss to follow-up), the need to initiate care contraindicated to study procedures and/or requirements, pregnancy, serious inter-current illness and if the study is cancelled due to other administrative reasons and/or unanticipated circumstances by the Sponsor of this study or the FDA. Additionally, the subject’s participation may be stopped without their consent if the military mission requires it or if the individual loses his/her DoD healthcare beneficiary status.

If the subject’s participation is stopped, the investigator will notify the subject and provide reason for doing so in person, by mail, email and/or telephone.

In the event that the subject withdraws and/or is withdrawn from the study before the completion of the Week 24 post-treatment assessment, he/she will be asked to come to the clinic for a final assessment of safety evaluations. If a subject withdraws before study completion, the reason for discontinuation will be captured on the appropriate eCRF page. Additionally, any data collected up until the time of subject withdrawal will be included in the final study analysis. (*Please see section 5.5.7 for additional information pertaining to biological specimens/withdrawal*)

Subjects who are withdrawn will not be replaced if they have received study treatment.

Additional Information:

Patient and Observer Scar Assessment Scale (POSAS)

The standard and comprehensive Patient and Observer Scar Assessment Scale (POSAS) [Draaijers LJ, et al., 2004] will be employed in this study, as a standard tool for capturing both the subject’s and two independent observer’s assessment of the scar post-treatment

[Idriss N, 2009]. Although many methods of rating scars exist, little consensus exists to dictate which method is optimal [Fearmonti R, et al., 2010, Durani P, et al., 2009]. Objective measures may be useful for evaluating a particular characteristic (e.g. color or elasticity), but these do not satisfactorily convey overall, clinically-relevant information about the scar as a whole [Brusselaers N, et al., 2010].

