5.7.3 Data and Statistical Analysis Plan

Due to the feasibility nature of this clinical trial, no formal statistical analysis nor interim analysis will be performed. Data collected in this study will be documented using summary tables. Quantitative variables will be summarized using descriptive statistics, including mean (and/or median), standard deviation (SD), and when appropriate minimum and maximum values. Categorical variables will be summarized by frequencies and percentages. Where appropriate, 95% confidence intervals either around the sample means or mean differences will be furnished. All data collected will be presented in subject data listings.

Power Analysis

Post hoc power analysis was conducted using G*Power 3.1 (Faul, Lang, & Buchner, 2007) for this 2 x 7 mixed design (i.e., two treatment groups x 7 waves of measurements). Given the constraints on sample size ($n = 20$), a power analysis was conducted with the intent to detect the obtained power ($1 - \beta$) given: (1) level of significance (set at $\alpha = .05$), effect size (standardized F statistic varied at .15, .2, and .25) and (3) rate of autocorrelation (average correlations of repeated measures varied at .3, .5, and .7). Even though ascertaining what constitutes a small/medium/large effect size is, in part, context and discipline-dependent, using Cohen's (2008) taxonomy of small ($F = .10$) and medium ($F = .25$) we see below that sufficient power (.80) to obtain significance for the 2 x 7 first order interaction will be obtained for a medium effect size when the autocorrelation is .5 or higher and for a slightly smaller effect size ($F = .2$) when autocorrelation approximates .7. However if the effect size approximates .15 sufficient

power will not be obtained, regardless of magnitude of autocorrelation.

AutoCorr	Effect Size	Power
0.3	0.25	0.729
0.5	0.25	0.881
0.7	0.25	0.989
0.3	0.2	0.503
0.5	0.2	0.672
0.7	0.2	0.904
0.3	0.15	0.286
0.5	0.15	0.399
0.7	0.15	0.639

Cohen (1988). *Statistical power analysis for the behavioral sciences*. (2nd Ed.). Hillsdale, NJ: Lawrence Erlbaum.

Proposed Analysis

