Nozzle blockage	
 • Nozzles designed with an aperture which allows for cells to pass through easily • 100 micron filtration occurs prior to spraying of cells • Spare nozzle supplied with each device
Nozzle aperture position	
 • IFU recommend test spray • IFU describes aperture positioning

The potential risks to the subject and adverse events associated with use of the ReCell Device discussed in the tables above are minor and easily controlled.

Adverse Event Evaluations and Reporting

Subjects will be monitored for safety from time of enrollment to conclusion of study visits. All adverse events will be collected by direct subject communication with investigator/study coordinator and review of source documents.

At each post-treatment visit, the research team will assess if the subject has experienced any adverse effects post-treatment with the investigational device. The subject will be asked if he/she has any problems, issues and/or concerns since the last encounter visit that could be potentially related to study participation. Any conditions or symptoms reported after the subject receives investigational product will be recorded as an adverse event (AE) on the AE eCRF. This includes new events after study device administration, conditions

that become more severe or increase in frequency, any disease-related signs or symptoms present at the Screening Pre-Treatment visit that have worsen in severity or frequency, as well as any event or finding that the Investigator feels is clinically significant.

Other treatment-related adverse events requiring surgical intervention prior to Week 12 post-treatment and all serious adverse event (SAE) occurrences will be treated and recorded in the eCRF. For all adverse events, the Investigator will provide an assessment of the event, its treatment resolution, and relationship to the investigational device. Subjects who have an ongoing AE related to the study device at Week 24 post-treatment will be followed for 30 days until resolution and/or stabilization of the event at a level acceptable to the Investigator.

Adverse Event Definitions:

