6.3 Actions to Minimize Risks

a. Safety Monitoring Plan

Based on trials conducted with the ReCell device, no significant participant risks are anticipated and no interim analysis is planned; therefore, there are no pre-specified stopping rule procedures planned for this clinical trial. However, if any serious safety issues do arise, medical judgment will be used and the Investigator will, in consultation with the Medical Research Monitor, the Sponsor, appropriate regulatory authorities, and/or IRB, take steps necessary to modify or discontinue the trial.

- b. Safety Analysis Plan:** The IRB, medical research monitor, and principal investigator will review any safety concern. A data safety monitoring board (DSMB) is not required for this study. Safety concerns will be analyzed by the PI and medical research monitor to avoid unnecessary exposure of subjects to ineffective or dangerous interventions. Patients may be discontinued from participation in the study in the presence of exclusion criteria or at the recommendation of the Principal Investigator or by the study medical research monitor ([name]).

The medical research monitor will function as an independent safety advocate for subjects enrolled into this clinical trial. The medical research monitor is required to review all unanticipated problems involving risk to subjects or others, SAEs, and all subject deaths associated with the protocol and provide an unbiased written report of the event. At a minimum the medical research monitor should comment on the outcomes of the event or problem and, in the case of a SAE or death, comment on the relationship to participation in the study. The medical research monitor should also indicate whether he concurs with the details of the report provided by the study investigator. Reports for events determined by either the investigator or medical research monitor to be possibly or definitely related to participation and reports of events resulting in death should be promptly forwarded to the IRB and/or ORP and USAMRMC CSSD PSSB (sponsor safety office).

c. Confidentiality Protection

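### Treated subjects may be withdrawn for outcome-related reasons with only a safety visit afterwards, and healing has no stated denominator, so the later comparisons can be biased in either direction

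*Combined protocol and SAP*

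**What the plan says.** **Withdrawal.** Section 5.5.4 (Subject Discontinuation and/or Withdrawal) says that the investigator may withdraw a subject for harm, protocol violations or non-compliance, and also for "the need to initiate care contraindicated to study procedures and/or requirements, pregnancy, serious inter-current illness". A subject who leaves before Week 24 is dealt with in one sentence: "he/she will be asked to come to the clinic for a final assessment of safety evaluations". Data gathered up to withdrawal go into the final analysis. Treated subjects are not replaced.

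**A second route.** Section 6.3 (Safety Analysis Plan) states: "Patients may be discontinued from participation in the study in the presence of exclusion criteria". It does not confine this to the period before surgery. Section 5.4 lists as an exclusion "The subject has active infection processes, that in the opinion of the investigator may compromise safety or study objectives". Infection is also one of the primary safety outcomes in Section 5.7.1.

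**Care limits after surgery.** Under Dressings in Section 5.5.4, negative pressure wound therapy "will not be reapplied after treatment with ReCell as this may compromise the treated area". Using a dressing other than the two named products on the treatment sites before healing is a deviation. The Infection paragraph of the same section gives daily cleaning and dressing of the wound as an example of infection care.

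**Adverse event follow-up.** Section 6.2: "Subjects who have an ongoing AE related to the study device at Week 24 post-treatment will be followed for 30 days". Nothing equivalent is given for a subject who leaves earlier.

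**Analysis.** In Section 5.7.3 the safety set is all enrolled subjects. The effectiveness set has no stated membership or denominator. A wound counts as healed if it reaches 95% re-epithelialization by Week 6. A seven-wave repeated measures ANOVA is planned, with no rule for incomplete subjects.

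**The concern.** ReCell is applied once, in the operating room. Needing non-protocol care afterwards is therefore no reason in itself to stop observing the subject, yet the text allows participation to end on that ground. Where the reason is an infection or a graft that needs other care, the missing data are related to the outcome.

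The within-patient design sharpens this. Withdrawal removes both regions, so a failure on one side also takes away the later result on the other. The bias could favour either treatment. The decision is discretionary, and the operating investigators, who open the envelope, know the allocation. Only the subject and the scar observers are described as blinded.

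Two things are at stake: the secondary effectiveness comparisons, and safety follow-up between an early exit and Week 24, although Specific Aim 1 promises monitoring through 24 weeks. Section 5.7.2 says that the results may be used to refine a pivotal trial.

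**Working it through.** **1. The plan's own figure.** The power table in Section 5.7.3 assumes 20 subjects and 7 waves. The matching calculation is a noncentral F with λ = f²·N·m/(1−ρ), df1 = 6 and df2 = (N−2)×6.
- N = 20, f = 0.25, ρ = 0.5: λ = 0.0625×20×7/0.5 = 17.5, df2 = 108, power 0.881, as printed. All nine cells agree within 0.001.
- If only subjects with all seven visits are analysed (an assumption; the plan is silent), N = 17 gives λ = 14.875, df2 = 90, power 0.809. N = 16 gives λ = 14, df2 = 84, power 0.778.

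The study is declared not prospectively powered, so this loss matters less than the bias. A complete-case ANOVA would also discard the visits before withdrawal that Section 5.5.4 promises to include.

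**2. What is kept and what can be lost.**

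| Item | Scheduled | After an early exit |
|---|---|---|
| Events recorded before or at exit | every visit | kept (safety set is all enrolled) |
| Wound and donor-site healing, patient POSAS | post-treatment visits | probably seen at the exit visit, since both fall under the safety outcomes; not afterwards |
| Observer POSAS, VSS, scar pain, satisfaction | Weeks 12 and 24 only | not requested |
| Post-treatment radiograph for heterotopic ossification | Week 24 only | not requested |
| Adverse events ongoing at exit | 30 days, only if device-related and ongoing at Week 24 | no stated follow-up |

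Section 5.7.3 classes missed visits that leave healing undetermined as a major deviation, but does not say what follows for the analysis.

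**3. How many subjects might be affected.** Section 6.2 gives risk bands. Taken per subject, with n = 20:
- Total graft loss, 5% to <10%: 20×0.05 = 1 to 20×0.10 = 2 (upper limit not reached). Chance of at least one: 1−0.95^20 = 64% to 1−0.90^20 = 88%.
- Infection, 1% to <5%: 0.2 to 1. Chance of at least one: 18% to 64%.
- Partial graft loss, 10% or more: 2 or more.

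Total loss plus infection, if they do not overlap, gives 1.2 to 3.0. Adding partial loss at 10% gives 3.2 to 5.0. These are counts of events, not of withdrawals.

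**4. Effect on healing, with assumed counts.** ReCell fails in 3 subjects and control in 1 other subject.
- All counted: 17/20 = 85% against 19/20 = 95%, difference −10 points.
- The 3 ReCell failures withdrawn before Week 6 and left out: 17/17 = 100% against 16/17 = 94.1%, difference +5.9 points.
- Mirror case (1 ReCell failure, 3 control failures, the control failures withdrawn and left out): 19/20 against 17/20 (+10 points) becomes 16/17 against 17/17 (−5.9 points).

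**5. Whether a denominator alone repairs it.** Return to the first case and count all 20. If the failed region is scored not healed and the other region's healing is known, the result is 17/20 against 19/20 (−10 points). If the other region is also scored not healed because it was not observed, control becomes (19−3)/20 = 16/20 and the difference is 17/20 − 16/20 = +5 points. A fixed denominator therefore has to go with continued observation by region.

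**The case against.** The strongest reply is that the primary outcomes are largely protected. Graft loss, infection and delayed healing are themselves safety outcomes. Data up to withdrawal are retained, the safety set is all enrolled subjects, discontinuations for adverse events are counted, and each premature termination is listed with reason and date. With 20 subjects and full listings, a failure seen before or at exit would be visible. This stands. A reader might infer that failures vanish from the study's results; the documents do not support that.

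A reader might also infer that infection or graft failure leads to withdrawal. Neither is a named ground. Section 5.5.4 describes managing infection within the study, Section 6.2 classes graft loss needing retreatment as a major treatment-related event rather than an exit, and both withdrawal clauses are permissive. The link runs through the infection exclusion, the contraindicated-care ground and the dressing rules. It is possible, not prescribed.

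Nor does withdrawal do nothing except stop data collection. Research biopsies at Weeks 2, 4 and 12 and the dressing limits continue after surgery, and withdrawal releases the subject from them. There can be good reason to stop those procedures. That does not require the scheduled non-invasive observation to end as well.

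Finally, the study is descriptive and the affected comparisons are secondary. That limits the weight of the point but does not answer it: a descriptive proportion with an open denominator can still mislead.

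**Conclusion.** The point holds in a limited form. A treated subject may be withdrawn at discretion for reasons that can be related to outcome. Only a safety visit is then requested, and no rule says how that subject counts towards healing. The secondary effectiveness comparisons and the late safety follow-up can be biased in either direction; safety events recorded up to exit are not lost.

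The swing from −10 to about +6 points is an illustration. It assumes 3 and 1 failures in different subjects, withdrawal of all three ReCell failures before Week 6, and their omission from the denominator, which the plan neither states nor rules out. The figure of 3 to 5 of 20 subjects is an upper illustration: it assumes non-overlapping events and includes partial graft loss, which nothing in the documents ties to withdrawal. The change is worth making because it is cheap and the data may inform a pivotal trial.

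**What to change.** 1. In Section 5.5.4, for subjects who have received study treatment, separate stopping study procedures (research biopsies, protocol dressings) from ending observation. Continue the scheduled non-invasive assessments and adverse event follow-up to Week 24 unless the subject withdraws consent or becomes unavailable.
2. State in Section 6.3 that the exclusion-criteria ground does not by itself end follow-up of a treated subject. Reconcile it with Section 5.4 and with the Dressings, Infection and Discontinuation text of Section 5.5.4. Which clinical rule applies is for the sponsor.
3. For those who do leave, define a region-level exit visit: wound and donor-site healing, photographs and patient POSAS, plus observer POSAS, VSS, scar pain and satisfaction where the wound has healed enough to score.
4. Apply the 30-day adverse event follow-up of Section 6.2 at early exit as well as at Week 24, for treatment-related events at either region or a donor site.
5. In Section 5.7.3, report healing over all treated subjects, by region. Show a region without a Week 6 status as not healed, and add a sensitivity analysis that takes regions not failed at exit as healed. State how incomplete subjects enter the ANOVA.

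The cost is protocol wording, a longer exit visit and some follow-up of subjects on non-protocol care. The visits are already in the schedule.

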5.5.5 Data Collection

Data management activities and statistical analytical support will be performed by the UPMC Center for Innovation in Restorative Medicine (CIRM) and its consultant, Glaser Consultants. With oversight provided by J. [name], CIRM will prepare a Data Management Plan (*see Appendix H*) and serve as the Data Coordinating Center (DCC) for all data management activities. The DCC will have no direct interaction or intervention with study subjects. The DCC will manage design, implementation and maintenance of the database, data entry, editing, ongoing quality control of the data, generation of reports, staff training, interval database access for investigative personnel, back-up and data security.

For this clinical trial, data will be collected at WRNMMC only then transcribed onto an electronic case report form (eCRF). No database is anticipated of data collected at WRNMMC; all data maintenance and analysis will occur only at CIRM.

Subject data collected for this research project will be entered into the Medrio electronic data entry system via use of a web browser. Medrio is commercially available software that provides an integrated eClinical Software as a Service (SaaS) platform with a fully hosted Electronic Data Capture (EDC) system. The Medrio system is a secure, regulatory compliant, web-based, electronic data capture tool designed to support research studies that requires an individualized password protected login in order to have access to the application.

The DCC/UPMC will secure the required educational license agreement (the University of Pittsburgh will serve as the educational institution of record) that is necessary, free of charge, for procurement of the Medrio system software tools to allow for database development. The DCC/UPMC will have sole ownership of the database. No parts of the database will be downloaded to the DoD network or devices.

Data will be collected from source documents and data collection forms designed in tandem with the protocol. Key datasets derived from the study protocol (*see Appendix L, Sample eCRF*) will be mirrored for database development by the DCC.

De-identified (coded) data collection entries into the Medrio system will occur on an ongoing basis during subject participation and will be performed by WRNMMC research team members only. Subjects will not be entering study specific questionnaire responses into the data entry system; they will be asked to complete a paper version handout.

Working from source documents and the data collection forms, the Research Coordinator will update the Medrio data management system within one week after each scheduled study visit for the subject.

All data collection activities will be monitored by IMARC Research, Inc.; qualified monitors, based on training and experience, will be assigned to this study as per Clinical Monitoring Plan (*see Appendix I*). Periodic onsite monitoring visits will be made to WRNMMC by the IMARC Research, Inc. clinical trial monitors to inspect the conduct of the study to determine if it is being executed according to the protocol and report their findings to the Sponsor. The monitors will assure that data is accurately captured on the eCRF and in agreement with source documentation; verify that investigational product is properly stored and accounted for, verify that subjects' consent for study participation has been properly obtained and documented, confirm that research subjects entered into the study meet inclusion and exclusion criteria, and assure that all essential documentation required by Good Clinical Practice (GCP) guidelines are appropriately filed.

In collaboration with Glaser Consultants, CIRM will perform all statistical analysis of intermittent data and upon completion of all subject visits.

The Investigator is responsible for maintaining any source documentation related to the study, including digital photographs of the donor sites and wound site treated with the investigational product, clinical laboratory data, radiographic imaging (x-ray results) for assessment of heterotopic ossification, histology analysis, informed consent forms and device accountability records.

a. Method of Collection from Study Participants:

Please refer to above Section 5.5.4

Please refer to CRF's included with this submission

The method for collection of clinical data from study participants by members of the study site personnel will be derived from interviews and assessments performed by the study investigator and/or coordinator during study visits. Study materials, information, photographs, radiographic imaging (x-ray results) for assessment of heterotopic ossification and biopsy samples obtained for the purpose of this clinical trial will be coded with the subjects assigned 3-digit study ID number. Listed below is data that will be collected at the following time points:

Screening/Pre-Treatment: Data collected will be information obtained from the subject's medical history including current medication use, allergies, information related to the traumatic injury, treatment with INTEGRA™ MBWM, demographic information, physical examination including height, weight and vital signs, pre-treatment photograph of treatment sites and donor sites, bloodwork for hematology/chemistry analysis, baseline pain and pruritus assessments at traumatic wound site using the POSAS tool, baseline radiographic imaging (x-ray results) for assessment of heterotopic ossification (if not previously obtained within 30 days of study enrollment), histological assessment and identification of randomized treatment

areas.

Surgical Procedure: Data collected will be: Wounds dimensions, the ReCell device lot number and expiration date, lot numbers (from inner and outer package box) for the enzyme and expiration date, information regarding device kit preparation for ReCell suspension and application, intervention photographs before treatment and after tissue removal, initial wound dressings, biopsy procedure information, and any device and/or surgical related problems or concerns, if any.

Acute Healing (Week 1, 2, 3, 4, and 6 post-treatment): Data collected will be atypical epithelialization (healing) characteristics at the wound and donor sites, wound dressing/treatment regimens, photography at the treatment and donor sites, biopsy for histology, scar pain/itching rating using the POSAS, results from routine laboratory tests obtained at Week 1 post-treatment, concomitant medication use and any adverse event occurrences; both subject reported and medical record review.

Long-term Outcome (Week 12 and 24 post-treatment): Data collected will be atypical epithelialization (healing) characteristics at the wound and donor sites, photography at the treatment and donor sites, radiographic imaging (x-ray results) for assessment of heterotopic ossification, biopsy for histology, scar pain/itching rating using the full POSAS (both Subject and Observer), scar assessment using the Vancouver Scar Scale, functional outcome rating questionnaire, patient satisfaction questionnaire results and any adverse event occurrences; both subject reported and medical record review.

- b. Source and Type of Data Collected from Existing Data Sources: Answer the questions below after considering the minimum necessary data required for the research study.
- i. Have you received a data consultation with a data expert to determine the data elements to be extracted or the data system to access? (Consulting with a data expert often saves time later in the compliance process because the data expert can advise on the data available in the numerous MHS data systems, the quality of that data and the methods for encrypting and collapsing data. You may contact a data expert at the following email address: [contact])
- ☐ Yes, then complete the questions in this subparagraph b according to the information received from the data consult
- X No, then complete the questions in this subparagraph b according to the best of your knowledge (**NOTE:** It is highly recommended to get a data consult).
- ii. Indicate whether you will receive a data extract from the MHS or will access a data system to create a data set. A data extract is when the MHS or a contractor provides the data set directly to the researcher. When receiving a data set through data extract, the researcher may indicate whether the data

elements should be provided as is, encrypted or collapsed. In contrast to a data extract, access to a data system means that the researcher may access a data system and create a data set for the research study.

☐ Data Extract X Access

- iii. Do you intend to use only a de-identified data set in your research study?

A de-identified data set is a data set that does not include any of the identifiers listed in the table in 5.5.5 (b)(vi). In addition, the researcher does not have actual knowledge of another way the data can be used alone or in combination with other known information to identify an individual. De-identified data is also data that a person, with appropriate knowledge of and experience with generally accepted statistical and scientific principles and methods for rendering information not individually identifiable, determines is not individually identifiable in accordance with the conditions outlined in 45 CFR 164.514 (b)(1).

☐ Yes X No

- iv. Will you need MHS data with health information?

Data with health information means any information that is created or received by the MHS that relates to the past, present or future physical or mental health or condition of an individual, the provision of health care to an individual or the past, present or future payment for the provision of health care to an individual. Examples of MHS data with health information includes data maintained on AHLTA, CHCS and ESSENTRIS.

X Yes ☐ No

- v. Do you intend to access a data base to obtain personally identifiable information that is not health information (PII)?

X Yes, will access data base for (PII)

☐ No, will not access data base for PII

- vi. Include the following table in your protocol and put an “x” in the MHS column next to the categories of data that you are requesting from the MHS. If you are planning to receive a data extract of MHS data that includes a data element that will be deidentified by the MHS, then you do not need to put an “X” in the column corresponding to the category of data for that data element.

	Study Participant	MHS	Other
1. Names	X		
2. Postal address with only town, city, State and zip code	X		

3. All geographic subdivisions smaller than a State, including street address, city, county, precinct, zip code and their equivalent geocodes, except for the initial three digits of a zip code if, according to the current publicly available data from the Bureau of Census: 1) the geographic unit formed by combining all zip codes with the same three initial digits contains more than 20,000 people; and 2) the initial three digits of a zip code for all such geographic units containing 20,000 or fewer people is changed to 000.			
4. All elements of dates (except year) for dates directly related to an individual, including birth date, admission date, discharge date, date of death; and all ages over 89 and all elements of dates (including year) indicative of such age, except that such ages and elements may be aggregated into a single category of age 90 or older	X	X	
5. Telephone numbers	X	X	
6. Fax numbers			
7. Electronic mail addresses	X		
8. Social security numbers (In accordance with the DoD Social Security Number Reduction Plan, please justify the reason for collecting the social security number of study participants in the space after xi.)	X	X	
9. Medical record numbers			
10. Health plan beneficiary numbers			
11. Account numbers			
12. Certificate/license numbers			
13. Vehicle identifiers and serial numbers, including license plate numbers			
14. Device identifiers and serial numbers		X	
15. Web Universal Resource Locators (URLS)			
16. Internet Protocol (IP) address numbers			
17. Biometric identifiers, including finger and voice prints			
18. Full face photographic images and any comparable images			
19. Any other unique identifying number, characteristic, or code (DEERs ID, EDIPN, Rank)			

vii. If you are requesting access to an MHS data system, put an “x” in the Request from MHS column next to the MHS system(s) from which you are

requesting data. If you do not know what system contains the elements you intend to request, please refer to the *Guide for DoD Researchers on Using MHS Data* or seek guidance from a data expert.

PHI Systems

MHS Data Systems	Request from MHS
AHLTA	X
CDM (from the MDR)	
CHCS	X
ESSENTRIS	X
PDTS	
TRAC2ES	
M2	
MDR	
PDHRA	
PDHA	
TMDS	
PEPR	
JTTR	

PII Systems Only

MHS Data Systems	Request from MHS
DMDC	N/A
MHS Learn	N/A
DMHRIS	N/A

De-Identified Data System

MHS Data Systems	Request from MHS
EAS	N/A

Other Systems

List Other system(s): N/A

viii. Do you intend to merge or otherwise associate requested data with data from any other sources outside of MHS, including other DoD sources that are not part of the MHS?

☐ Yes, will merge data X No, will not merge data

ix. Using the tables in 5.5.5 (b) (vi), put an “x” in the Other column next to the categories of data or data elements that include the data elements you intend to merge. *Not Applicable*

- x. Is there any possibility that the data will become identifiable because of triangulation, a small cell size, or any unique data element(s)?

Triangulation means using different data elements that are not themselves identifiable but that in combination can be used to determine the identity of an individual. For example, triangulation would be using rank and race together to determine the identity of an individual with a particular health condition.

Small cell size means that the categories contain a small number of eligible individuals that satisfy the category description. Guidance for acceptable cell size is available from the Centers for Medicare and Medicaid Services. For example, the rank category of five star generals with a particular diagnosis may be less than 30 so the data category may need to include lower ranks too.

A unique data element includes any unique features that are not explicitly enumerated in the categories of data in Table vi above, but that could be used to identify an individual. Examples of unique data elements include 1) a unique number, such as a medical record number or EDIPN; 2) a unique code, such as a diagnosis code or a bar code on electronic health record; and 3) any unique characteristic, such as a high rank like general or admiral or a unique race or gender with another unique characteristic.

☐ Yes, there is a reasonable possibility the data will become identifiable.

X No, there is no reasonable possibility the data will become identifiable.

- xi. Please justify the reason for collecting the social security number of study participants.

We will collect the last four digits of the participants social security number for the purpose of accessing the medical record for chart review and verification of study data collected.

